4.2. Lifestyle Considerations

4.2.1. Meals and Dietary Restrictions

Study drug can be consumed whole or crushed and sprinkled on food. For administration at home, study drug should be taken with food. Study drug may be consumed up to 30 minutes after food, if necessary. If a participant has not consumed study drug within 30 minutes after food, the participant should consume study drug with a snack.

Participants will be advised to refrain from consumption of grapefruit, grapefruit juice, or any fruits that are known to be strong CYP3A4 inhibitors (e.g., pomegranate) from 1 day before the first dose of study drug until after the final dose.

4.2.2. Activity

Participants must abstain from strenuous exercise for 8 hours before each study visit. Strenuous exercise might cause temporary spikes in biomarkers that could confound analysis of the effect of study drug.

4.2.3. Contraception Guidelines

4.2.3.1. Contraception Guidelines for Male Participants

Males capable of reproduction enrolling in this study must meet ONE of the following contraceptive criteria from Screening until 90 days after the last dose of study drug:

1. Is sexually abstinent from penile-vaginal intercourse as his usual and preferred lifestyle (abstinent on a long-term and persistent basis) and agrees to remain abstinent from Screening until 90 days after the last dose of study drug.
2. Agrees to use a male condom AND female partner uses/has in place one of the following highly effective contraceptive methods from Screening until 90 days after the last dose of study drug:
 - a. Combined hormonal contraception (containing estrogen and progesterone) associated with inhibition of ovulation: oral, intravaginal, or transdermal
 - b. Progesterone-only hormonal contraception associated with inhibition of ovulation: oral, injectable, or implantable
 - c. Intrauterine device (IUD)
 - d. Intrauterine system (IUS)
 - e. Bilateral tubal occlusion.

4.2.3.2. Contraception Guidelines for Female Participants

Females of childbearing potential enrolling in this study must meet ONE of the following contraceptive criteria from Screening until 30 days after the last dose of study drug:

1. Is sexually abstinent from penile-vaginal intercourse as her usual and preferred lifestyle (abstinent on a long-term and persistent basis) and agrees to remain abstinent from Screening until 30 days after the last dose of study drug.
2. Must have a negative serum pregnancy test at Screening and negative urine pregnancy tests at all protocol-specified timepoints. Agrees to use one of the following highly effective contraceptive methods, which must be in place from at least 1 month before Screening until 30 days after the last dose of study drug:

- a. Combined hormonal contraception (containing estrogen and progesterone) associated with inhibition of ovulation: oral, intravaginal, or transdermal. Any hormonal contraception containing ethinyl estradiol must contain <20 mcg ethinyl estradiol.
- b. Progesterone-only hormonal contraception associated with inhibition of ovulation: oral, injectable, or implantable
- c. IUD
- d. IUS.

4.3. Screen Failures

Screen failures are defined as participants who consent to participate but are not subsequently enrolled in a study cohort. Minimal information, including demography, screen failure details, and eligibility criteria is required to ensure transparent reporting of screen failures to meet the Consolidated Standards of Reporting Trials (CONSORT) publishing requirements and to respond to queries from regulatory authorities.

Individuals who do not meet the following criteria for participation in the study may be rescreened according to the following guideline (Note: The Investigator will first consult with the MM regarding such individuals):

1. Individuals on incompatible or excluded concomitant medications may be rescreened after an appropriate washout period (e.g., 30 days or 5 half-lives, whichever is longer).
2. Individuals who have an exclusionary laboratory value during the Screening Period may be retested before the start of the Treatment Period if the Investigator believes that the prior laboratory value is not consistent with the individual's overall clinical picture.

5. STUDY TREATMENT

Details about the physical, chemical, and pharmaceutical properties of tildacerfont are provided in the IB.

5.1. Treatment Administration

Participants will be treated with oral tildacerfont QD for 12 weeks (Cohorts 1 to 3) or BID for 4 weeks (Cohorts 4 to 9).

Pediatric age and weight-based tildacerfont dose levels are defined in [Table 2](#). For each dose level, the amount of study drug that a participant will receive will depend on the participant's age and body weight at Screening according to [Table 2](#).

Cohort 1 will be dosed at the equivalent of the adult 50 mg dose. Cohort 2 will receive the equivalent of the adult dose of 200 mg. If needed based on a safety concern in participants in Cohort 1, an interim dose Cohort 1a may be included. Cohort 3 will dose no higher than Cohort 2 (or Cohort 1a) but enroll up to approximately 10 participants in the younger age group of 2- to 10- years.

Cohorts 4, 6, and 7 will dose at the 200 mg adult dose equivalent BID; and Cohort 5, 8 and 9 will dose at up to 400 mg adult dose equivalent twice per day. Based on DMC recommendation and Sponsor decision, taking into account all available safety and exposure data, Cohorts 5, 8 and 9 may be initiated at 300mg adult equivalent BID for approximately 5 participants each, and then another approximately 5 may be enrolled in each at 400mg adult equivalent BID after DMC review.

Table 2. Tildacerfont Dose Levels and Pediatric Weight-Based Dosing

Weight at Screening (kg)	50 mg QD adult equivalent dose	100 mg QD adult equivalent dose	200 mg QD or BID adult equivalent dose	300mg BID adult equivalent dose	400 mg BID adult equivalent dose
Age group: 2- to 5-years					
13 to 14.1	25	50	75	100	150
14.1 to <21.2	25	50	75	100	150
21.2 to <26.1	25	50	100	150	200
26.1 to <31.8	25	75	100	150	200
31.8 to <33.9	25	75	150	150	300
≥33.9	50	100	150	150	300
Age group: 6- to 10-years					
20 to <23.7	25	50	75	100	150
23.7 to <29.9	25	50	100	150	200
29.9 to <35.5	25	75	100	150	200
35.5 to <39.2	25	75	150	200	300
39.2 to <47.5	50	100	150	200	300
≥47.5	50	100	200	300	400
Age group: 11- to 17-years					
26 to <30.5	25	50	75	100	150
30.5 to <39.2	25	50	100	150	200
39.2 to <45.7	25	75	100	150	200
45.7 to <53.4	25	75	150	200	300
53.4 to <61	50	100	150	200	300
≥61	50	100	200	300	400

Abbreviations: QD=once daily.

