The adult exposure levels observed after 2 weeks of treatment were extrapolated to pediatric participants based on body weight and age for this study using a PBPK approach based on healthy adults. The PBPK model was based on *in vitro* and *in vivo* information on the metabolism and PK of tildacerfont and was validated using the plasma concentration-time profiles in healthy adults in the fed state. To account for differing CYP3A4 expression by age, the Upreti ontogeny profile was used in the pediatric dose predictions in three age groups, 2 to 5, 6 to 10, and 11 to 17 ([Upreti and Walhstrom 2016](#)). Pediatric doses on a mg/kg basis were predicted by age group to correspond to the adult exposures at the same dose levels. Within the lower dose cohorts (50 mg and 100 mg), dose bands were constructed such that participants would not receive a dose greater than 20% over the predicted mg/kg conversion. Weight bands were constructed such that participants in higher dose cohorts would not receive a dose greater than 10% over the predicted mg/kg conversion of the corresponding adult dose.

Preliminary PK data from Cohorts 1-3 show that the PBPK model overestimates drug exposure in children, such that the weight-based adult equivalent doses utilized in the children do not provide the exposures observed in adults. Additionally, an inverse relationship between age and exposure is apparent. This may be due to differences in drug metabolism across developmental stages, specifically CYP enzyme activity which is the primary driver of tildacerfont elimination. CYP enzyme activity peaks in early childhood and declines into adulthood. Consequently, children sometimes require relatively higher doses than adults to achieve optimal exposures of drugs that are eliminated by CYP-dependent metabolism (i.e., the Upreti ontogeny profile may not have adequately adjusted for physiologic differences that impact tildacerfont exposure).

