3.1.3. Extension Period

Participants who complete the 12- or 4-week treatment period, depending on cohort, may be eligible to continue dosing to complete 2 years on treatment in an extension study. Participants will sign a separate informed consent form at Week 12 or Week 4. Pending DMC review, participants in Cohorts 1 and 1a (if indicated) will receive the adult equivalent dose of 200 mg QD during the extension (i.e., Cohort 1 participants will immediately switch to 200 mg equivalent if the DMC has already recommended this dose for Cohort 2, or participants may enter the extension period on 50 mg equivalent and increase to 200 mg equivalent after such a recommendation is made). If a Cohort 1-3 participant is to dose escalate to the 200 mg equivalent, they may do so at the next scheduled visit or come to the clinic for an unscheduled visit and pick up their new supply of study drug. Participants will receive a follow-up phone call 2 weeks after dose escalation to check for AEs.

Further tildacerfont dose adjustments may occur during the extension on a case-by-case basis at the discretion of the Investigator with Sponsor approval. Any extension participant may receive the highest dose recommended by the DMC for their age group. Dose changes (increase or decrease) may occur at a scheduled visit, an unscheduled visit, or via a phone visit, but any dose escalation > 200mg QD will be followed by safety labs (link to list) within 2-4 weeks of the change. Once all participants are in the extension period, safety- data will be reviewed every 6 months by the DMC. Weight-based dose adjustments may be made at any extension visit, with no follow-up labs required.

For Cohorts 1-3, the first visit of the extension will be Week 12. For Cohorts 4-9, Week 4 will be the first extension visit, followed by extension clinic visits at Weeks 8 and 12 (\pm 2 weeks). Starting at Week 12, all participants will attend clinic visits every 12 weeks (\pm 2 weeks).

Approximately a 12-week supply of study drug, as appropriate, will be dispensed at each visit. Approximately 30 days after the last dose of study drug, participants will have a final follow-up visit conducted by telephone. Concomitant medications and AEs will be reviewed. If any ongoing safety issues are identified, the participant may be asked to visit the clinic for additional tests, labs, or assessments.

The extension study visits will include the following:

- Review concomitant medications for any changes

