- Physical exam (abbreviated/directed)
- Vital signs: blood pressure, pulse rate, body temperature, respiration rate, and weight
- Safety labs (see [Appendix 2](#) and [Appendix 4](#))
- Pregnancy test for FOCP (urine)
- Urinalysis (Weeks 48 and 96 only)
- Pharmacodynamics (ACTH, 17-OHP, A4, testosterone, and 11KT) drawn prior to GC dosing at approximately 8 AM (\pm 1 hour). Fasting is not required.
- Tildacerfont concentration (single sample)

SPR001-205
Spruce Biosciences, Inc.

CLINICAL STUDY PROTOCOL
Version 5.0

- Study drug accountability
- Suicidality Questionnaire- C-SSRS since last visit (participants aged ≥ 6 years only)
- Depression and Anxiety Questionnaires (PROMIS or SWYC depending on age of participant)
- GC dosing adjustments
- Assess for AEs
- Bone age and predicted adult height calculated from X-ray image of left hand and wrist (every 6 months if deemed appropriate by Investigator, see [Appendix 2](#) and [Appendix 4](#)).
- Tildacerfont dose adjustment as needed (based on recommendation of investigator or due to weight-based dosing changes)

4. STUDY POPULATION**4.1. Eligibility Criteria****4.1.1. Inclusion Criteria**

A participant must meet all of the following criteria to be eligible for this study:

1. Male and female participants aged 2- to 10-years (Cohorts 3, 7, and 9), 11- to -17 years (Cohorts 1, 1a, 2, 6, and 8), and ≥ 18 years (Cohorts 4 and 5) at Screening.
2. For participants aged 2 to 5 years, a minimum weight at Screening of 11 kg.
3. Has a known childhood diagnosis of classic CAH due to 21-hydroxylase deficiency (21-OHD) based on genetic mutation in CYP21A2 and/or documented (at any time) elevated 17-OHP and currently treated with hydrocortisone (HC), HC acetate, prednisone, prednisolone, methylprednisolone (or a combination of these). Other types of CAH may be allowed with Sponsor approval.
4. For participants in Cohorts 4-9, $1.2X \text{ ULN} < A4 < 4X \text{ ULN}$. A4 values outside of this range may be allowed with Medical Monitor (MM) approval.
5. A stable dose of GC replacement for ≥ 1 month before Screening without evidence of non-adherence (as assessed by Investigator). Weight-based dose adjustments or stress dosing in the month prior to Screening are not exclusionary but should be discussed with the MM.
6. For participants on mineralocorticoid replacement, a stable dose for ≥ 1 month prior to Screening.

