8.3.4. Safety Analyses

The Safety Population will be used for all safety analyses. Safety data will be listed by participant and summarized by adult equivalent dose levels (50, 100, 200 mg QD; and 200 mg, possibly 300 and/or 400 mg BID) using the frequency of event or descriptive statistical summaries, as appropriate. Listings and summary tables will be provided for AEs, clinical laboratory tests, vital signs, and ECG data. Urinalysis, psychiatric evaluations, concomitant medications, and physical examinations will be presented in listings only.

A DMC will review accumulating safety information by cohort. Refer to [Section 9.4.4](#) for information on the DMC.

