## 19 APPENDIX C: TILDACERFONT DOSE LEVELS AND PEDIATRIC WEIGHT-BASED DOSING

**Table 13 Tildacerfont Dose Levels and Pediatric Weight-Based Dosing**

Weight	50 mg QD adult equivalent dose	100 mg QD adult equivalent dose	200 mg QD or BID adult equivalent dose	300mg BID adult equivalent dose	400 mg BID adult equivalent dose
Age group: 2- to 5-years					
13 to 14.1	25	50	75	100	150
14.1 to <21.2	25	50	75	100	150
21.2 to <26.1	25	50	100	150	200
26.1 to <31.8	25	75	100	150	200
31.8 to <33.9	25	75	150	200	300
≥ 33.9	50	100	150	200	300
Age group: 6- to 10-years					
20 to <23.7	25	50	75	100	150
23.7 to <29.9	25	50	100	150	200
29.9 to <35.5	25	75	100	150	200
35.5 to <39.2	25	75	150	200	300
39.2 to <47.5	50	100	150	200	300
≥47.5	50	100	200	300	400
Age group: 11- to 17-years					
26 to <30.5	25	50	75	100	150
30.5 to <39.2	25	50	100	150	200
39.2 to <45.7	25	75	100	150	200
45.7 to <53.4	25	75	150	200	300
53.4 to <61	50	100	150	200	300
≥61	50	100	200	300	400

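### Protocol Table 2 gives 2- to 5-year-olds of 31.8 kg or more the same dose at the 300 mg BID level as at 200 mg (the SAP prints a higher one), and eligible children of 11 to <13 kg have no dose row

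*Protocol*

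**What the plan says.** Protocol Section 5.1 sets the dose by age and Screening weight according to Table 2. In the 2- to 5-year block, the row for 31.8 to <33.9 kg is "31.8 to <33.9 25 75 150 150 300". The row for 33.9 kg and above also has 150 mg in both the 200 mg and the 300 mg columns. SAP Appendix C, Table 13, has "31.8 to <33.9 25 75 150 200 300" for the first of these weights and also 200 mg in the 300 mg column for the second. SAP Section 5.2.1 refers to Table 13 for the dose.

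Protocol Section 1.2.3 explains that bands at the higher doses were built so that a child "would not receive a dose greater than 10% over the predicted mg/kg conversion of the corresponding adult dose". It does not print the conversion.

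The 300 mg level may be used in Cohort 9 (ages 2 to 10 years): Cohorts 5, 8 and 9 "may be initiated at 300mg adult equivalent BID for approximately 5 participants each". It can also be reached in the extension, where "Any extension participant may receive the highest dose recommended by the DMC for their age group" (Protocol Section 3.1.3).

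On eligibility, Protocol Section 4.1.1 states: "For participants aged 2 to 5 years, a minimum weight at Screening of 11 kg". The lowest 2- to 5-year row, in both documents, is "13 to 14.1 25 50 75 100 150".

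**The concern.** Two documents give different milligram doses for the same child, and nothing in them settles which is right. The SAP precedence clause (SAP Section 4) covers planned analyses, not dispensing. SAP Section 15, which lists departures from the protocol, does not mention the difference. Since Protocol Table 2 assigns the dose, the 300 mg level as written is no escalation for these children.

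Three things are at stake.

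- **Escalation.** The DMC reviews 300 mg data before recommending 400 mg. A child in this band gives it no information above the 200 mg BID dose for that weight, and then faces a doubling.
- **Tabulation.** Under Protocol Section 8.3.4, "Safety data will be listed by participant and summarized by adult equivalent dose levels". The child's adverse events would be counted at a level whose dose was not received.
- **Dosing of the smallest children.** A site can enrol a child of 11 to <13 kg and have no dose to give. Extending the lowest row downward, the obvious improvisation, would push the mg/kg dose up.

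**Working it through.** No sample size or error rate is involved; the check is of the tables themselves.

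**1. Comparing the two tables.** Inputs: the 18 weight rows by 5 dose columns in Protocol Table 2 and SAP Table 13. Exactly two dose cells differ, both in the 300 mg column for ages 2 to 5 years:

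| Weight (kg) | 200 mg level | 300 mg level, protocol | 300 mg level, SAP | 400 mg level |
|---|---|---|---|---|
| 31.8 to <33.9 | 150 | 150 | 200 | 300 |
| 33.9 and above | 150 | 150 | 200 | 300 |

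Per day (BID), the difference is 300 mg against 400 mg.

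**2. Step pattern in the protocol table.**
- 400 mg column / 200 mg column = 2.0 in all 18 rows.
- 300 mg column / 200 mg column = 1.33 or 1.5 in 16 rows, and 150/150 = 1.0 in the two disputed rows. With the SAP value it is 200/150 = 1.33.
- The rule of 1.5 times the 200 mg cell, rounded down to a multiple of 50 mg, gives 75 → 112.5 → 100; 100 → 150; 150 → 225 → 200; 200 → 300. It reproduces 16 of 18 protocol rows and 18 of 18 SAP rows. The two misses are the disputed cells.
- The disputed rows run 150 → 150 → 300 mg.

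**3. Age ordering.** In the 200 mg column, 150 mg starts at 31.8 kg for ages 2 to 5 and at 35.5 kg for ages 6 to 10, so the younger group is never dosed lower at the same weight. In the protocol's 300 mg column, a 5-year-old of 36 kg gets 150 mg and a 6-year-old of 36 kg gets 200 mg. That runs against the faster-clearance argument in Protocol Section 1.2.3.

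**4. Would 200 mg be too much?**
- 150/31.8 = 4.72 mg/kg; 200/31.8 = 6.29 mg/kg.
- The protocol's 300 mg column already allows 150/21.2 = 7.08 mg/kg in the same age group.
- Assumption: the 2- to 5-year band edges (100/21.2 = 150/31.8 = 4.72 mg/kg) sit at 110% of the predicted dose, and prediction scales in proportion to dose. Predicted at 200 mg: 4.717/1.1 = 4.29 mg/kg. Predicted at 300 mg: 1.5 × 4.288 = 6.43 mg/kg, with a ceiling of 1.5 × 4.717 = 7.08 mg/kg. At 31.8 kg, 200 mg is then about 2% below prediction (6.29/6.43) and 150 mg about 27% below (4.72/6.43).

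**5. Weight gap.** The eligibility floor is 11 kg and the table floor 13 kg, so 11 to <13 kg is uncovered at all five dose levels. If the 75 mg cell (200 mg level) were extended downward:
- at 11 kg, 75/11 = 6.82 mg/kg, 45% above the 4.72 mg/kg step-up point (6.82/4.72 = 1.45);
- at 13 kg, already covered by the table, 75/13 = 5.77 mg/kg, 22% above it (5.77/4.72 = 1.22);
- by contrast, 50 mg at 11 kg would be 4.55 mg/kg, 4% below it.

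The 6- to 10-year and 11- to 17-year blocks start at 20 and 26 kg, and the inclusion criteria set no matching floor for either group.

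**The case against.** The case for treating this as minor is that the two cells matter only if Cohort 9 opens, if it is run at 300 mg rather than directly at 400 mg, and if it includes a 2- to 5-year-old of at least 31.8 kg. The extension route needs a DMC-recommended dose for the age group and Sponsor approval. The error lowers the dose and does not breach the 10% rule, which caps only over-dosing. Nor is 150 mg at about 32 kg an unusual 300 mg-level dose: a 6- to 10-year-old of 29.9 to <35.5 kg also gets 150 mg, which is 4.24 mg/kg at 35.4 kg. Any mislabel is traceable, because the milligram dose is on the eCRF, mg/kg is listed (SAP Sections 9.4.15 and 12.1), and treatment-emergent events are also tabulated by cohort (SAP Section 14.1). Extension analyses belong to a separate SAP.

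All of that stands, and it limits the consequence. It does not explain why a child of fixed age and weight should get no increase between two named dose levels, or why the two documents disagree.

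On the weight gap, the 45% figure rests on reading the band edges as the cap, and the table's own lowest rows already exceed that value. This is a fair criticism of the figure, and also a reason to check those rows. The Pharmacy Manual was not available and might address small children, but Protocol Section 5.1 names Table 2 as the dosing rule. A missing row may well produce a query rather than a wrong dose; the protocol should still not admit a child it cannot dose.

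**Conclusion.** Both defects are present as written.

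**Dose cells.** Protocol Table 2 and SAP Table 13 conflict in two cells, 150 against 200 mg per dose. The protocol value gives no escalation from 200 to 300 mg BID and a doubling at the next step. The internal pattern favours 200 mg, but the documents do not confirm it. Reach is small: at most the 2- to 5-year-olds of 31.8 kg or more among about 5 children in an optional stage, possibly none, plus any extension participants in that band.

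**Weight gap.** Children of 11 to <13 kg are eligible without a dose. The gap now matters mainly for Cohorts 7 and 9, since Protocol Section 1.2.3 reports 30 children already in Cohorts 1-3 by 1 November 2023. How many children fall in the gap is unknown.

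The cell mismatch and the missing row are read directly from the tables and need no assumption. The comparisons with a predicted or step-up mg/kg value depend on the band edges reflecting the 10% cap. Neither defect can be repaired at analysis, so both need settling before the dosing they affect.

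**What to change.** 1. Before 300 mg BID is used in 2- to 5-year-olds, check the two cells against the predicted mg/kg conversion and the 10% cap, and correct whichever table is wrong. Do not adopt 200 mg on the pattern alone.
2. Before a child under 13 kg is dosed, either raise the floor in inclusion criterion 2 to 13 kg, or add an 11 to <13 kg row derived from the conversion rather than by extending the 75 mg cell. Check the existing lowest 2- to 5-year rows at the same time.
3. Give the 6- to 10-year and 11- to 17-year groups weight floors that match their tables, or add rows.

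The cost is one protocol clarification or amendment and, if needed, a corrected SAP table. Raising the floor excludes the smallest 2- to 5-year-olds; adding a row requires a dose check by clinical pharmacology.

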5.2. Preparation/Handling/Storage/Accountability

5.2.1. Acquisition and Accountability

The Investigator is responsible for study drug receipt and accountability, reconciliation, and record maintenance.

5.2.2. Formulation, Appearance, Packaging, and Labeling

Tildacerfont will be provided in bottles of 25 mg, 50 mg and 200 mg tablets. Each bottle will be labeled with the product name, strength, lot number, recommended storage conditions, name of the Sponsor, and an Investigational Use Statement (e.g., "Caution: New Drug – Limited by Federal [USA] Law to Investigational Use"). Labeling will comply with all legal requirements and supply no information about individual participants.

